## **5 Image Analysis**

### **5.1 Lesion size evaluation:**

- 5.1.1 A patient must have a single intraaxial brain lesion of 5 mm or greater for study inclusion as measured on either T2-weighted or T1-post contrast weighted imaging.
- 5.1.2 Lesions will be measured on either axial T2 FLAIR weighted or T1 post-contrast imaging on a slice displaying the maximal lesion size using the longest diameter after appropriate magnification on the picture archiving and communicating system (PACS) monitors.
- 5.1.3 For patients with multiple lesions appropriate for study assessment, the five (5) largest lesions will be assessed.

### **5.2 Lesion CNR evaluation:**

- 5.2.1 The largest circular ROI that fits within the lesion on axial T1 post-contrast imaging will be placed and will define the lesion ROI.
- 5.2.2 The ROI mean signal intensity will be recorded.
- 5.2.3 A mirror ROI will be placed in the contralateral normal-appearing white matter and used as the "background" mean signal intensity measurement.
- 5.2.4 An extracranial ROI without visible artifact will be used as the "noise" mean signal intensity measurement.

### **5.3 Quantitative MRI**

- 5.3.1 The largest circular ROI that fits within the lesion on axial T1 post-contrast imaging will be placed and will define the lesion ROI.
- 5.3.2 The T1 and T2 tissue weighting that maximizes the ROI mean signal intensity will be identified.
- 5.3.3 A mirror ROI will be placed in the contralateral normal-appearing white matter and used as the "background" mean signal intensity measurement.
- 5.3.4 An extracranial ROI without visible artifact will be used as the mean "noise" signal intensity measurement.

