## 1 OBJECTIVES

### 1.1 Primary Objectives

- 1.1.1. To estimate the contrast-to-noise ratio (CNR) for several imaging modalities in brain malignancy as compared with normal brain parenchyma separately by type of malignancy and treatment status. The methods to be studied include Quantitative MRI (T1 and T2 sequencing), Chemical Exchange Saturation Transfer (CEST) MRI, Multiple B-Value Diffusion Imaging (Adv Diff), and Multiple inversion time (TI) arterial spin labeling (ASL) perfusion imaging (Adv ASL).

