## 2.3 Quantitative MRI

Intensity values on routine MR imaging are not defined in terms of any consistent scale since the signal is dependent on many hardware and patient-specific factors. Hence there is very little gained in measuring the “bright” or “dark” pixel values on an MR image, and the images must be interpreted subjectively. [22] This would be analogous to subjectively describing “hot” or “cold” spots on an infrared heat map image when the absolute temperature scale of the pixels is not known. This study proposes to use multi-parameter mapping to quantitatively measure the signal changes in the tissues to address these challenges. In MR imaging, hydrogen nuclei or “spins” are the sources of the signal. In the strong magnetic field of an MR scanner, these spins emit RF signals in response to transmitted RF pulses. Thus, contrast mechanisms in MR imaging are highly dependent on the hydrogen spin density or proton density (PD), as well as the longitudinal and transverse relaxation times (T1 and T2, respectively), which tend to vary between different tissues or fluids. However, measurement of relaxation times requires multiple acquisitions, and as a result, measurement or quantitation of these parameters can be excessively long for clinical MR exam.

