Recent developments in rapid multi-parameter mapping techniques are possible due to advances in accelerated imaging and reconstruction techniques. [22, 23] These typically incorporate efficient pulse sequence designs and mathematical constraints to assess the desired information in each pixel. SyntheticMR developed the first clinically available method and released by GE Healthcare as "MAGIC" (MAGnetic resonance Image Compilation), which can achieve whole-brain quantitation in 5-6 minutes. [24] The SyntheticMR method assumes the process of T1 and T2 relaxation times to be monoexponential, whereas it may be multi-exponential for many tissues. However, a phantom study has revealed good accuracy and reproducibility for T1, T2, and PD measurements by the SyntheticMR method. These measured parameters can also be applied to an MR spin model produce images with almost any contrast weighting by virtually changing repetition time (TR), echo time (TE), and inversion time (TI). Synthetic MRI is particularly useful when many different contrast settings (for example, T1 weighted imaging (WI), T2WI, proton density WI) are required. Synthetic MRI of the brain without the use of a contrast agent has been reported to produce images that although inferior in image quality the diagnostic power of the images was comparable to that of images obtained via conventional MRI sequences. [25] Therefore, if the diagnostic power of images obtained via synthetic MRI after administration of a contrast agent is also proved to be comparable to that of conventional MRI, synthetic MRI could be a useful means of screening for brain metastases, significantly reducing scan time and providing quantitative data. [26]

Multiple investigators have also demonstrated CEST imaging at UHF. These results indicate the potential utility of amide proton transfer (APT) at the high field as a noninvasive biomarker of white matter pathology, providing complementary information to other MRI methods in current clinical use. Also, contrary to results obtained at lower fields, APT imaging at 7T revealed significant contrast between white and gray matters, with a higher APT signal apparent within the white matter. These findings suggest that UHF CEST imaging would be sensitive to alterations in the APT signal related to both malignancies and treatment-related changes. [27]

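### Section 5.3 meets the CNR objective but takes quantitative MRI only from signal on a weighting chosen to maximise lesion signal, and never records the T1 or T2 values that motivate the method

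*Combined protocol and SAP*

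**What the plan says.** The primary objective (1.1) is to estimate CNR by tumour type and treatment status for four methods: "The methods to be studied include Quantitative MRI (T1 and T2 sequencing"), CEST, multi-b-value diffusion and multi-TI ASL.

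The background in 2.3 explains why quantitative MRI is among them. It states that "Intensity values on routine MR imaging are not defined in terms of any consistent scale" and adds that measuring bright or dark pixels gains little. Its answer is: "This study proposes to use multi-parameter mapping to quantitatively measure the signal changes in the tissues to address these challenges". It then cites a phantom study showing "good accuracy and reproducibility for T1, T2, and PD measurements by the SyntheticMR method". It also gives a second use: "These measured parameters can also be applied to an MR spin model produce images with almost any contrast weighting".

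Section 5.3 sets out the measurement. First, "The largest circular ROI that fits within the lesion on axial T1 post-contrast imaging will be placed and will define the lesion ROI". Then, "The T1 and T2 tissue weighting that maximizes the ROI mean signal intensity will be identified". A mirror region in contralateral white matter supplies the background signal and an extracranial region supplies the noise signal.

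Section 7.3 allows a CNR or an equivalent parameter for each method, without naming the equivalent for any of them. Section 7.4 reports the CNR for each method with a 95% confidence interval.

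**The concern.** The reason given for the method and the measurement prescribed for it do not line up. Mapping is introduced because it measures tissue properties on a physical scale, yet what 5.3 keeps is signal intensity at a selected weighting. Three things follow.

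- **No T1 or T2 readout.** The quantities that a different site or scanner could most readily compare are not a planned output.
- **A weighting that may vary.** The maximisation in 5.3.2 is over the lesion region and no common weighting is fixed. A group mean CNR may therefore average lesions seen at different image contrasts.
- **The wrong target for a contrast endpoint.** The rule maximises lesion signal, but CNR depends on the difference between lesion and background.

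At stake is how interpretable and reusable the result is for one of the four primary methods. Whether a CNR can be computed at all is not in question.

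**Working it through.** **1. What each method section records**

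| Section | Method | Lesion and mirror values | Noise region |
|---|---|---|---|
| 5.3 | Quantitative MRI | Signal intensity at the selected weighting | Yes |
| 5.4 | CEST | Mean signal on processed CEST data | Yes |
| 5.5 | Diffusion | AKC and ADC | No |
| 5.6 | ASL | CBF; BAT is also assessed | No |

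The methods split two and two. Diffusion and ASL have physical values and no noise region, so the alternative to CNR in 7.3 fits them naturally. Section 5.3 is laid out for CNR and names no alternative. No other section, including 7.3 and 7.4, calls for T1, T2 or proton density in any region.

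**2. The plan's own precision figures**

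The only ones are for CEST (7.3: mean 14.9, SD 3.0). With mean ± 1.96 × SD/√n:

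- n = 20: 14.9 ± 1.96 × 3.0/√20 = 13.59 to 16.21 (stated 13.6 to 16.2).
- n = 45: 14.9 ± 1.96 × 3.0/√45 = 14.02 to 15.78 (stated 14.0 to 15.8).

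Both reproduce. They do not bear on this point: the documents give no mean or SD for a quantitative-MRI CNR, T1 or T2, so no precision for those can be derived.

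**3. Is maximising lesion signal the same as maximising contrast?**

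This is an illustration only. None of the tissue values comes from the documents. The spin-echo model is S = PD × (1 − exp(−TR/T1)) × exp(−TE/T2), searched over TR 0.3 to 10 s and TE 10 to 150 ms. Assumed white matter: PD 0.70, T1 1.2 s, T2 45 ms. In all three assumed lesions, lesion signal peaked at TR 10 s and TE 10 ms.

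| Assumed lesion (PD, T1, T2) | Contrast at maximum lesion signal | Maximum contrast (TE; TR 10 s) | Ratio |
|---|---|---|---|
| 0.80, 1.6 s, 60 ms | 0.1155 | 0.1251 (27.5 ms) | 0.92 |
| 0.85, 2.0 s, 80 ms | 0.1847 | 0.2244 (40 ms) | 0.82 |
| 0.90, 2.5 s, 120 ms | 0.2525 | 0.3525 (55 ms) | 0.72 |

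Worked example, second row: the lesion at TE 10 ms is 0.85 × (1 − e^−5) × e^−0.125 = 0.7451; white matter is 0.70 × (1 − e^−8.33) × e^−0.222 = 0.5604; the difference is 0.1847. At TE 40 ms the same formula gives 0.2244, and 0.1847/0.2244 = 0.82.

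Two limits apply. The comparison is of contrast, with noise treated as constant across weightings. And the signal maximum fell at the same corner of the grid for all three lesions, so the illustration shows that the rule misses the contrast optimum; it does not show that the chosen weighting will differ between lesions. That second possibility rests on the text alone, which fixes neither a common weighting nor a permitted range.

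**The case against.** The strongest reply is that 5.3 does what 1.1 asks. The objective is CNR, 5.3 supplies lesion, background and noise regions, and 7.4 reports the CNR. Section 2.3 also gives synthetic weighting as a use of the maps, so selecting a weighting is consistent with part of the rationale. All of this stands: the gap is between 5.3 and the main argument of 2.3, not between 5.3 and 1.1.

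Three stronger readings might be inferred, and the documents do not support them.

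- **That the method yields only the arbitrary-scale quantity that 2.3 rejects.** Section 2.3 criticises raw pixel values. A CNR takes lesion, background and noise from the same image, so a common scale factor cancels. The dependence on the chosen weighting does not cancel.
- **That quantitative MRI alone discards its physical values.** CEST in 5.4 also records signal only.
- **That T1 and T2 would be lost.** Under 6.4 and section 8, images are held on servers at the imaging site and in REDCap, and study data are kept permanently. If maps are generated, the values could be read later. What is lost is prespecification.

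It is also fair to say that the wording of 7.3 does not exclude T1 and T2, and that 5.3.2 does not state whether the weighting is chosen per lesion or once overall. Both are reasons to write the rule down.

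**Conclusion.** The point holds in a limited form. Section 5.3 serves the CNR objective, but it bases this method on a weighting selected from the lesion's own signal, by a rule that does not target contrast, and it plans no T1 or T2 value. Recording those values would give the method an output that does not depend on the weighting and would deliver the purpose stated in 2.3.

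The change is worth making, but the primary objective does not fail without it. The size cannot be derived from the documents; the 72% to 92% range depends on the assumed tissue values, the spin-echo model and constant noise. That the weighting is synthetic and may be lesion-specific is a reading of 5.3.2 alongside 2.3, well supported but not stated outright.

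**What to change.** - **In 5.3:** record mean T1 and T2 from the maps in the lesion and mirror regions, and proton density if it is mapped. State whether the maps are acquired before or after contrast. Section 4.4 lists the sequence without saying, and T1 values cannot be interpreted without it.
- **In 7.3 and 7.4:** name the within-patient lesion-minus-mirror differences in T1 and T2 as the equivalent parameter for quantitative MRI, reported by group with a 95% confidence interval beside the CNR.
- **In 5.3.2:** if the synthetic-image CNR is kept, replace the signal-maximising rule with one prespecified weighting for all lesions. Adding T1 and T2 alone would leave the weighting problem in place.

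The cost is wording in three sections, a few more readings per lesion in regions already drawn, and a few more reported quantities. No extra scan is needed if the sequence already outputs T1 and T2 maps. The documents imply this but do not confirm it, so it should be checked first.

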#### **5.4 CEST MRI**

- 5.4.1 The largest circular ROI that fits within the lesion on axial T1 post-contrast imaging will be placed and will define the lesion ROI.
- 5.4.2 The mean signal intensity for a corresponding ROI location on the processed CEST data will be recorded.
- 5.4.3 A mirror ROI will be placed in the contralateral normal-appearing white matter on the processed CEST data will be used as the “background” mean signal intensity measurement.
- 5.4.4 An extracranial ROI without visible artifact will be used as the “noise” mean signal intensity measurement.

#### **5.5 Multiple B Value Diffusion Imaging (Adv Diff)**

- 5.5.1 The largest circular ROI that fits within the lesion on axial T1 post-contrast imaging will be placed and will define the lesion ROI.
- 5.5.2 The AKC for the lesion will be determined using B-values of 0, 1000, and 2000 mm^2/s.
- 5.5.3 The ADC of the lesion will also be determined using B-values of 0 and 1000 mm^2/s.
- 5.5.4 A mirror ROI will be placed in the contralateral normal-appearing white matter, and “background” AKC and ADC measurement will be measured.

#### **5.6 Adv ASL**

- 5.6.1 The largest circular ROI that fits within the lesion on axial T1 post-contrast imaging will be placed and will define the lesion ROI.
- 5.6.2 This ROI will be used to assess the cerebral blood flow (CBF) from the processed ASL data.
- 5.6.3 A mirror ROI will be placed in the contralateral normal-appearing white matter for assessment of the “background” CBF.
- 5.6.4 This ROI will be used to assess the bolus arrival time (BAT) from the processed ASL data.

## 5.7 Task-based fMRI

- 5.7.1 fMRI data will be analyzed using custom software, IClinfMRI.
- 5.7.2 The general linear model will be used to generate an activation t-value map for each task-based fMRI data. The model includes the convolution of the task paradigms with a canonical hemodynamic response function.
- 5.7.3 Significantly activated areas will be determined by thresholding the t-value map at corrected  $P < .05$ .

## 5.8 Resting-state fMRI

- 5.8.1 Resting-state datasets will be pre-processed through slice timing, motion correction, despiking, detrending, regressing out covariates (including six motion parameters and two averaged fluctuations over masks of white matter and cerebrospinal fluid), band-pass filtering of 0.01-0.08 Hz, and 4-mm FWHM smoothing.
- 5.8.2 Functional connectivity maps will be generated by using both seed-based analysis and independent component analysis.
- 5.8.3 For the seed-based analysis, seed locations will be determined by anatomical motor and language areas with the assistance of a regional homogeneity map.
- 5.8.4 For the independent component analysis, 30-50 independent components will be determined, and the relevant functional connectivity maps will be determined with template matching and inspection by neuroradiologists.

## 5.9 Radiation planning validation

- 5.9.1 A 3D T1 SPACE sequence will be obtained to validate the ability of UHF MRI to provide acceptable levels of geometric distortion for radiation therapy planning purposes.
- 5.9.2 The specific parameters of the sequence will be optimized to maximize contrast and minimize artifact and distortion.
- 5.9.3 The geometric distortion will be evaluated with a full-field geometric distortion phantom to assess the geometric accuracy of the SPACE sequence with its specific parameters.
- 5.9.4 For radiation therapy purposes, the geometric distortion of less than 1mm is desired for the typical head field of view and 2 mm is the targeted limit for the useable field of view

## 6 Patient Information Confidentiality Plan

### 6.1 Collection of Identifiers:

The patient identifiers that will be collected in this study consist of patient medical record numbers and dates. Electronic data will be kept securely at MD Anderson (password protected behind the institution firewall).

The study will be performed following institutional policies for the use of existing medical information for research. Confidentiality will be maintained throughout the study. No identifying information will be used in any publication from this study. Electronic study data will be stored on password-protected institution computers behind the institution firewall. Only the PI and collaborators who have completed Human Subject Protection Training (HSPT) will have access to the study data.

### 6.2 Training of personnel:

Only MDACC personnel designated by the PI who have completed HSPT training will have access to study records. These personnel will be fully trained to maintain patient health information confidentiality.

### 6.3 Data Storage:

Electronic study data will be kept on password-protected computers behind the institution firewall. Paper records (data forms, and unique identifiers, etc.) will be kept in a locked file cabinet with access granted only to study investigators and research staff.

### 6.4 Data Sharing:

Study will utilize REDCap to store and share data with study collaborators and research staff with HMRI. Only authorized members of research team from MDA & HMRI who signed the delegation of authority log will have access to the data in REDCap.

Study data will be collected and managed using the REDCap (Research Electronic Data Capture) system hosted at MD Anderson. REDCap ([www.project-redcap.org](http://www.project-redcap.org)) is a secure, web-based application with controlled access designed to support data capture for research studies, providing: 1) an intuitive interface for validated data entry; 2) audit trails for tracking data manipulation and export procedures; 3) automated export procedures for seamless downloads to common statistical packages; and 4) procedures for importing data from external sources.

REDCap (<https://redcap.mdanderson.org>) is hosted on a secure server by MD Anderson Cancer Center's Department of Oncology Care & Research Information Systems. REDCap has undergone an annual Governance Risk & Compliance Assessment (since May 2014) by MD Anderson's Information Security Office and found to be compliant with HIPAA, Texas Administrative Codes 202-203, University of Texas Policy 165, federal regulations outlined in 21CFR Part 11, and UTMDACC Institutional Policy #ADM0335.

Those having access to the data include the study PI and research team personnel at MDA & HMRI. Internal users are authenticated against MDACC's Active Directory system. External

# Proprietary Information of MD Anderson

Protocol No: 2019-1032

Version No: 10

Version Date: August 25, 2023

users will be granted access to the study. The application is accessed through Secure Socket Layer (SSL). The linking of patient protected health information (PHI) will be removed from the data when it is exported from REDCap for final analysis. All dates for a given subject will be shifted by a randomly generated number between 0 and 364, thus preserving the distance between dates. Dates for each subject will be shifted by a different randomly generated number.

The digital imaging data will be stored on secure servers held by HMRI. Access to these research images in the HMRI will be restricted to [name], [name] or the authorized research personnel at HMRI who will oversee the release of research MRI images of this IRB protocol and shared with [name], Principal Investigator of this IRB protocol: 2019-1032. Complete confidentiality will be maintained; the investigators will be responsible for the transmission, sharing and storage of research imaging data.

## 6.5 Final Disposition of study records:

After publication, any printed paper records will be placed into the Shred-it confidential waste bins for disposition. The study will be performed following current institutional standards for the use of existing medical information, banking the data, and identifiers for research. There will be no further use of the study data without prior review and approval by the IRB.

## 7 STATISTICAL CONSIDERATIONS

### 7.1 Definitions

7.1.1 Lesion “**treatment response**” will be defined by size and contrast to noise ratio (CNR). Treatment response will be assessed only in patients with treatment prior to enrollment.

7.1.1.1 Size – treatment response in a single lesion will be considered as a decrease in size of 30%. (see section 5.1)

7.1.1.2 CNR—treatment response will be considered as a decrease in T1 post-contrast CNR of at least 20%. (see section 5.2) by standard T1 post-contrast imaging.

7.1.1.3 Lesions that do not meet these criteria for treatment response will be considered treatment failure.

7.1.2 Disease **recurrence** will be determined by surgical pathology (if available) or at least three months of imaging follow-up. Disease recurrence will be assessed only in patients with treatment prior to enrollment. Imaging findings will be considered recurrent disease in a lesion if:

7.1.2.1 The lesion was initially considered to be a treatment responder.

7.1.2.2 The lesion showed a successive increase in the size of 25% from nadir or a single imaging time point increase of 40%. (see section 5.1)

7.1.2.3 Lesions that do not meet these criteria will be considered radiation necrosis.

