## 4 STUDY PLAN/DESIGN

### 4.1 Patient Enrollment:

Patients being evaluated for treatment of a suspected brain malignancy at MD Anderson Cancer Center will be screened for eligibility based on their screening diagnostic MRI scan and available clinical information. Once eligibility is confirmed, patients will be approached for protocol introduction and consenting and enrollment. Attempts will be made to scan patients in the 7T system within 30 days of an MRI scan performed at either 3T or 1.5T.

Up to twenty (20) healthy volunteers will be recruited through local advertisement for the purposes of MRI sequence optimization. Volunteers will be scanned in accordance with the UTMDACC Division of Diagnostic Imaging Policy # 3.00: Imaging of Healthy Volunteers for Quality Assurance/Improvement and Technical Development.

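### Section 7.1.1 leaves open whether treatment response needs both a size and a CNR change or only one, and its CNR arm does not require matched scans

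*Combined protocol and SAP*

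**What the plan says.** Section 7.1.1 applies only to patients treated before enrollment and says that lesion response "will be defined by size and contrast to noise ratio (CNR"). Two sub-items follow, each worded as a complete definition. In 7.1.1.1, "treatment response in a single lesion will be considered as a decrease in size of 30" percent. In 7.1.1.2, "treatment response will be considered as a decrease in T1 post-contrast CNR of at least 20" percent, measured "by standard T1 post-contrast imaging". Section 7.1.1.3 closes the list: "Lesions that do not meet these criteria for treatment response will be considered treatment failure".

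The label is then used in three places:
- Section 7.4 compares CNR between responding and non-responding lesions with a Wilcoxon rank-sum test, if enough follow-up images exist.
- Section 7.1.2.1 makes responder status a condition for recurrence on imaging: "The lesion was initially considered to be a treatment responder".
- Section 7.1.2.3 assigns the remainder: "Lesions that do not meet these criteria will be considered radiation necrosis".

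On the images themselves, section 4.6.1 plans one 7T session per patient and bases response and recurrence on standard-of-care follow-up scans. It does not fix scanner, field strength or sequence. Section 4.1 aims to place the 7T scan "within 30 days of an MRI scan performed at either 3T or 1.5T", so both lower field strengths are in clinical use. Section 5.2 takes the noise value from one extracranial region.

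**The concern.** Two analysts could follow this text and label the same lesion differently. If both changes are required, a lesion that shrinks by 40% with a 10% fall in CNR is a treatment failure. If either suffices, a lesion that grows while its CNR falls by 20% is a responder. In both cases the label contradicts one of the plan's own two measures, and the plan has no category for disagreement.

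The CNR arm adds a second problem. Section 2.3 says that signal intensities on routine MR have no consistent scale, and section 2 lists higher CNR among the advantages of 7T over 1.5T and 3T. Despite this, 7.1.1.2 applies a fixed percentage threshold across scans that need not match.

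The reference scan is not named either. Treatment precedes enrollment, and section 3.1 requires new or increasing signal after treatment. The pre-treatment scan, the eligibility scan and the 7T scan are therefore all candidate baselines.

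At stake are the responder comparison in 7.4 and the radiation necrosis versus progression contrast behind the secondary objective (1.2.1). Without pathology, a lesion not labelled a responder cannot be recurrent and, read literally, 7.1.2.3 makes it radiation necrosis. Section 7.4 draws that contrast from initial responders, so the label also decides which lesions enter it.

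**Working it through.** **The plan's own figures.** The documents give no figure for the response rule. The only CNR precision figure, in 7.3, reproduces: 14.9 ± 1.96 × 3.0/√20 = 13.6 to 16.2, and with n = 45, 14.0 to 15.8. The implied CV, 3.0/14.9 = 20%, is between patients for CEST. It is not a test-retest CV and is not used below.

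**Number of lesions.** Sections 3.3 and 7.3 give 100 patients, 90% with tumor and about half treated: 100 × 0.90 × 0.5 = 45. I take one (largest) lesion per patient, all with usable follow-up.

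**Labels that depend on the reading.** Let p_s and p_c be the proportions meeting the size and CNR rules, and φ their correlation.

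P(both) = p_s·p_c + φ√[p_s(1−p_s)p_c(1−p_c)]; P(either) = p_s + p_c − P(both).

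Assume p_s = 0.30 and p_c = 0.40.

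| φ | Both | Either | Discordant |
|---|---|---|---|
| 0 | 0.12 × 45 = 5.4 | 0.58 × 45 = 26.1 | 20.7 |
| 0.5 | (0.12 + 0.5 × √0.0504) × 45 = 0.2322 × 45 = 10.5 | 0.4678 × 45 = 21.0 | 10.6 |

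With size rates of 20% to 40%, CNR rates of 30% to 50% and φ from 0 to 0.5, discordant lesions number about 9 to 22.5 of 45.

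**Noise value.** Section 5.2 gives no CNR formula. I assume lesion-to-background difference divided by noise. If the difference is unchanged, a 25% rise in the noise value gives 1/1.25 = 0.80, which is a 20% fall.

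**Fall of at least 20% with no true change, same scanner.** Assume independent errors with within-lesion CV c.
- Normal model: P = Φ(−0.2/(c√1.64)), because follow-up minus 0.8 × baseline has mean 0.2 and variance c²(1 + 0.64), in units of the true CNR.
- Lognormal model: P = Φ(ln 0.8/(√2·√ln(1 + c²))).

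| Assumed c | Normal | Lognormal | Expected of 45 (normal) |
|---|---|---|---|
| 5% | 0.1% | 0.1% | 0.0 |
| 10% | 5.9% | 5.7% | 2.7 |
| 15% | 14.9% | 14.5% | 6.7 |
| 20% | 21.7% | 21.3% | 9.8 |

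The normal-model chance stays below 5% only if c is under 0.2/(√1.64 × 1.645) = 9.5%.

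**Systematic scanner effect.** If a change of scanner multiplies CNR by r, P = Φ(−(r − 0.8)/(c√(r² + 0.64))). With an assumed r = 0.9, this is 4.8%, 20.3%, 29.0% and 33.9% at the same four CVs. With r = 0.8 it is 50% at any CV.

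**The case against.** The strongest reply is that the text already leans one way. The conjunction in 7.1.1 and the plural reference to criteria in 7.1.1.3 both favor requiring both changes, so one clarifying sentence might be enough. The direction of the wording is conceded. It still does not say what to do with a discordant lesion beyond calling it a failure, and the free-standing definitions in 7.1.1.1 and 7.1.1.2 remain.

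The sizes rest on assumptions. The documents give no response rates, no correlation between the two measures and no test-retest CV. Two measures of one lesion are probably positively correlated, so independence is the unfavorable end. At a CV of 5% on one scanner the noise problem is negligible. The scan-matching evidence also has limits: the 3T or 1.5T statement in 4.1 concerns the clinical scan near the 7T session, and the reference to standard imaging in 7.1.1.2 may mean clinical scans at both time points. A scanner change is possible under 4.6.1, but nothing shows how often it would occur.

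A reader might infer more than the documents support:
- **Response and recurrence on the same scan.** Sections 7.1.2.1 and 7.4 put response first and growth afterwards, so this is not what the plan describes.
- **A dark lesion that starts to enhance counts as a responder.** That needs an absolute CNR, which section 5.2 does not specify. With a signed CNR the value would rise.
- **A set percentage fall from a 3T-to-1.5T change.** Section 2 says only that CNR is higher at 7T, with no amount.
- **The CNR criterion should be deleted.** That would replace the sponsor's definition. Size alone has a similar gap, since 5.1.2 allows measurement on either T2 FLAIR or T1 post-contrast images.

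**Conclusion.** The point holds as an internal inconsistency with a practical consequence. Sections 7.1.1 to 7.1.1.3 do not fix one response rule, and they force discordant lesions into a label that one of the two measures contradicts. At the assumed 30% and 40% rates, roughly 11 to 21 of 45 labels depend on the reading; other plausible rates move this range. Separately, an unmatched CNR comparison can produce a qualifying fall without any change in the lesion. The chance runs from about 0.1% to 21% over assumed CVs of 5% to 20%, so no fixed error rate can be claimed.

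Discordance is not proof of mislabelling, because the plan has no reference standard for response. Nor must the effect be dilution. For T1 post-contrast CNR, the 7.4 comparison is partly circular, since the groups are defined in part by a fall in that same quantity, and the difference could be inflated.

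The effect is confined to the response comparison and to the recurrence and necrosis labels that follow from it. The primary CNR estimates and their confidence intervals are unaffected, and 7.4 makes the response analysis conditional on enough follow-up.

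**What to change.** Reconcile 7.1.1 with 7.1.1.1 to 7.1.1.3 before any response label is assigned:
1. State whether response needs both changes or either one. The choice is the sponsor's.
2. Name the reference scan for the size and CNR changes.
3. Count a CNR change towards the label only when both scans share field strength and protocol. Otherwise record the lesion as not evaluable on CNR.
4. Report lesions that meet one criterion but not the other as a separate category, and repeat the 7.4 responder comparison under the other reading as a sensitivity analysis.

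The cost is an amendment to the wording, plus a record of field strength and protocol for each scan used. No extra imaging is needed. The downside is that some lesions without matched scans cannot be evaluated on CNR, which reduces the number available for a comparison that already depends on follow-up.
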